
Schedule of Visits
	
 1 Assessment and Roll-in (2-weeks prior to procedure) 2 Index Procedure 3 1-Week post-procedure (\pm 2 days) 4 2-Week post-procedure (\pm 2 days) 5 3-Week post-procedure (\pm 2 days) 6 4-Week post-procedure (\pm 2 days) 7 5-Week post-procedure (\pm 2 days) 8 6-Week post-procedure (\pm 2 days) 9 7-Week post-procedure (\pm 2 days) 10 8-Week post-procedure (\pm 2 days) 11 9-Week post-procedure (\pm 2 days) 12 10-Week post-procedure (\pm 2 days) 13 11-Week post-procedure (\pm 2 days)

	
14 12-Week post-procedure (\pm 2 days)
 
15 Confirmation: 13-Week post-procedure (\pm 2 days)
 
All subjects will be offered a \$25 gift card for completing weekly follow-up during the treatment phase.

Study Duration	1 Year
Assessment Tools	
Ankle Brachial Index
 
HbA1c
 
Monofilament test for neuropathy
 
Photograph
 
E-Z Graph Wound Assessment System
 
Sf-36v2 Health Survey

Primary Endpoint	Proportion of subjects who have a closed wound at or before 12 weeks after the index procedure.
Primary Hypothesis	
As an observational study, there is no formal hypothesis test. The precision of the estimate of the proportion of subjects who successfully close will be determined.
 
Assumptions:
 
 • A minimum 50 subjects • A 95% Confidence Interval of the estimate • A 2-sided confidence interval • Using exact Clopper-Pearson estimation 
The Confidence Intervals (CI) at selected success rates are as follows:
 
 • @ 25%; CI = 25.4% Boundaries 13.8%-39.3% • @ 50%; CI = 28.9% Boundaries 35.5%-64.5% • @ 75%; CI = 25.4% Boundaries 60.7%-86.2% 
Thus, a sample size of 50 should allow for a reasonable estimate of treatment success at 12 weeks and for reasonable comparisons to historical controls.

Statistical Analysis	
Descriptive statistics including but not limited to mean, standard deviation, frequency and percentages will be used to describe demographics, medical history, and characterize baseline variable as appropriate.
 
A Z-test will be used to assess whether the proportion of subjects that were successful is greater than zero. Kaplan-Meier analysis will be used describe the survival curve assuming complete closure as the event of interest. A repeated measure ANOVA will be used to assess changes in, wound area and quality of life over time.

TABLE OF CONTENTS

1	Background	13

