4.3 Secondary Objectives

Some secondary objectives include but are not limited to:

- Describe the time course to full wound closure
- Determine the subjects' quality of life score before and after treatment
- Characterize the safety profile of MIRODERM and the procedure
- Explore the histological characteristics of those who successfully heal and those who don't

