6.2 Sample Size, Subject Participation, and study Duration

This study will enroll up to 50 and no more than 65 subjects over 6 months. Single centers may continue to enroll until a maximum of 25% (13 subjects) of the planned minimum sample size or until, across all centers, the total sample size is reached. Subject participation will be approximately 9.0 to 15.0 Weeks from time of recruitment to study completion at 1) one-week following assessment of wound closer or 2) following 12 weeks of treatment. In both cases subjects will be discontinued from the study per protocol.

Subjects who do not complete the study per protocol may be exited from the study in the following manner:

- Subject presents with osteomyelitis or an infection of the study of the study DFU
- Subject voluntarily withdraws consent.
- Subject lost-to-follow-up
- Subject death

Subjects have the right to withdraw from the study at any time, for any reason or no reason, without jeopardizing their medical care.

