6.7.2 Wound assessment and size documentation

Wound will be assessed for gross dimensions and infection. If an infection is an AE form should be completed and ***the subject will be discontinued from the study.***

The area of the wound will be documented using the E-Z Graph Wound Assessment System and photography.

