6.9 Study Exit

Subjects will be discontinued from the study per protocol. Under the following circumstances:

- Subject's index wound has been determined to be fully closed and remains closed at their 1-week follow-up confirmation
- Subject had completed their 12-week post-treatment follow-up and their index wound has not completely healed
- Subject presents with osteomyelitis of the study DFU or an infection of the study DFU
- Subject voluntarily withdraws consent.
- Subject lost-to-follow-up
- Subject death

When a subject is study exited, patients are no longer considered participants in the study and have no further obligations under the protocol. patients may undergo continued care as deemed appropriate by physician of record.

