7 STATISTICAL CONSIDERATIONS

As a prospective clinical outcome and survivorship study, there are no specific hypotheses to be tested. Data analysis may be conducted intermittently as needed or as requested by investigators without a power penalty and consist primarily of summary statistics and inferential statistics for changes in dependent measures over time.

Specific data analyses may include but are not limited to:

- **Demographics** and other pre-treatment characteristics will be summarized and characterized with appropriate descriptive statistics including error measures. Statistics may include mean, mode, median, range, inter-quartile range, minimum, maximum, frequency, cumulative frequency percentage and cumulative percentage. Results may be presented in a narrative and graphically.
- **Subject reported and dependent outcome measures** will be summarized and thoroughly characterized with the appropriate descriptive statistics including error measures. Statistics may include mean, mode, median, range, inter-quartile range, minimum, maximum, frequency, cumulative frequency percentage and cumulative percentage. Results may be presented in a narrative and graphically. Measures collected at multiple timepoints will also be analyzed using inferential statistics to assess changes over time, of special interest post-treatment changes from pre-treatment values. As appropriate a repeated measure ANOVA or Wilcoxon signed rank

test will be completed for each outcome measure. If a significant trend is identified, significance among time points may be further explored using the appropriate pair-wise comparisons. In all cases a p-value equal to or less than 0.05 will be considered significant. No corrections for multiple pair-wise comparisons will be made.

Missing data will be ignored in statistical calculations while using the appropriate n (sample size) for any given statistic or test.

Sample Size Justification: The precision of the estimate of the proportion of subjects who successfully close will be determined.

Assumptions:

- A minimum 50 subjects
- A 95% Confidence Interval of the estimate
- A 2-sided confidence interval
- Using exact Clopper-Pearson estimation

The Confidence Intervals (CI) at selected success rates are as follows:

- @ 25%; CI = 25.4% Boundaries 13.8%-39.3%
- @ 50%; CI = 28.9% Boundaries 35.5%-64.5%
- @ 75%; CI = 25.4% Boundaries 60.7%-86.2%

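### Time to closure is to be described by plain Kaplan-Meier with no censoring or competing-event rule; under the method's default, exits for infection, osteomyelitis or death would push the closure curve upward

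*Combined protocol and SAP*

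**What the plan says.** The method appears once, in the Statistical Analysis row of the Study Synopsis: "Kaplan-Meier analysis will be used describe the survival curve assuming complete closure as the event of interest". Section 7 (Statistical Considerations) does not name Kaplan-Meier. The curve serves the first secondary objective in section 4.3, "Describe the time course to full wound closure".

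Section 6.9 (Study Exit) lists these reasons, among others, for leaving the study: "Subject presents with osteomyelitis of the study DFU or an infection of the study DFU" and "Subject death". Section 6.7.2 makes the infection exit mandatory: when infection is found at a follow-up visit, "the subject will be discontinued from the study". Section 6.2 puts the same exits in one list with withdrawal and loss to follow-up, under "Subjects who do not complete the study per protocol may be exited from the study in the following manner". On what happens next, section 6.9 says: "When a subject is study exited, patients are no longer considered participants in the study and have no further obligations under the protocol".

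The only rule that touches incomplete follow-up is in section 7: "Missing data will be ignored in statistical calculations while using the appropriate n (sample size) for any given statistic or test". It does not say how any exit reason enters a time-to-event analysis.

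**The concern.** Kaplan-Meier with a single event type treats every other departure as censoring. It assumes that those who left would have gone on to close at the same rate as those still followed. After death that is impossible. After removal because the study ulcer became infected it is implausible, and closure on study can no longer happen. Each such exit shrinks the risk set, so later closures count for more than one subject's share.

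Section 3 gives a full description of the time course to closure as part of the study's rationale. The trial has one arm, and the plan intends comparisons with historical controls and the literature. No concurrent arm shares an upward shift, so any shift favours the device. The curve is also a separate estimator from the primary proportion, so correcting the denominator of that proportion would leave the curve unchanged.

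**Working it through.** **1. The plan's own figures.** The plan states no figure for the curve. Its only statistical figures are the exact Clopper-Pearson intervals at n = 50. With x = 50p, the limits are the beta quantiles B(0.025; x, 51 − x) and B(0.975; x + 1, 50 − x).

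- 25% (x = 12.5): 13.84% to 39.26%
- 50% (x = 25): 35.53% to 64.47%
- 75% (x = 37.5): 60.74% to 86.16%

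These reproduce the stated limits. The three closure rates are used again below.

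**2. Direction.** In week w let r be the number at risk and d the number closing.

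- Kaplan-Meier: 1-KM = 1 − Π(1 − d/r) = Σ S_KM(w−1) · d/r, where S_KM falls only at closures.
- Aalen-Johansen: CIF = Σ S_all(w−1) · d/r, where S_all falls at closures and at competing exits. With no other censoring this equals (total closures)/n.

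S_KM is never below S_all, so 1-KM ≥ CIF. The inequality is strict as soon as a closure follows an exit.

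**3. Worked example, n = 50 with 25 closures.** Assumed closures in weeks 1 to 12: 0, 1, 2, 2, 3, 3, 3, 3, 2, 2, 2, 2. The on-study proportion is 25/50 = 50.0%. With one exit in each of weeks 1 to 5, the Kaplan-Meier survival is

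(48/49)(45/47)(42/44)(38/41) × (34/37)(31/34)(28/31)(26/28)(24/26)(22/24)(20/22) = 0.4485, so 1-KM = 55.1%.

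| Exits (assumed) | 1-KM at week 12 |
|---|---|
| None | 50.0% |
| 5, weeks 1–5 | 55.1% |
| 10, weeks 1–5 | 61.7% |
| 5, weeks 8–12 | 51.4% |
| 5, kept at risk as not closed to week 12 | 50.0% |

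**4. Range over exit rates.** The documents name infection and osteomyelitis as risks (section 5.1) but give no rate, so 4%, 10% and 20% are assumptions. Take a constant weekly closure probability a and a weekly exit probability b among those not closing, and let q = (1 − a)(1 − b). Then

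- CIF = a(1 − q¹²)/(1 − q)
- 1-KM = 1 − (1 − a)¹²

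For 50% closure and 10% exits, a = 0.06126 and b = 0.01305, so q = 0.9265 and q¹² = 0.400. CIF = 0.06126 × 0.600/0.0735 = 0.500, and 1-KM = 1 − 0.93874¹² = 0.532. The early pattern puts all exits in weeks 1–6 and all closures from week 4 on.

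| True closure on study | Exits | 1-KM, constant rates | 1-KM, early exits |
|---|---|---|---|
| 25% | 4% | 25.5% | 25.9% |
| 25% | 10% | 26.4% | 27.5% |
| 25% | 20% | 28.0% | 30.6% |
| 50% | 4% | 51.2% | 51.9% |
| 50% | 10% | 53.2% | 55.1% |
| 50% | 20% | 57.2% | 61.6% |
| 75% | 4% | 77.2% | 78.0% |
| 75% | 10% | 80.9% | 83.0% |
| 75% | 20% | 90.0% | 93.3% |

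If every exit comes after the last closure (closures in weeks 1–8, exits in weeks 9–12), 1-KM is 50.0% and the excess is zero.

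**5. Check by simulation.** With n = 50, 4,000 replicates, true closure of 50% and closures uniform over weeks 1–12, exits of 10% and 20% give 53.3% and 57.1% when uniform over weeks 1–12. They give 54.7% and 60.6% when confined to weeks 1–6. The two approaches agree.

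Infection found at the treatment visit before application does not enter the curve, because section 6.6.4 counts subjects as enrolled only after treatment.

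**The case against.** The strongest reply is that the plan nowhere says these exits are censored. A statistician could keep them in the risk set as not closed to week 12, which fits the synopsis sentence and, absent other censoring, gives no excess. That stands. A reader might infer that the plan prescribes a biased curve; the documents support only that no rule is given and that the method's ordinary use produces the excess.

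A reader might also infer that the plan counts these exits as treatment failures. It does not: section 6.2 groups them with withdrawal and loss to follow-up. An infected ulcer may close after exit, whereas death rules closure out. The excess is therefore measured against closure on study, a target the plan should name.

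A third tempting reading is that the curve must contradict the primary proportion. That holds if exits count as not closed, but the plan has no such rule. If section 7's missing-data sentence were read as dropping exits, 25 closures with 5 or 10 exits would give 25/45 = 55.6% or 25/40 = 62.5%. Both are above the constant-rate Kaplan-Meier values of 53.2% and 57.2%.

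Finally, nothing in the documents supports a rate as high as 20%, and eligibility excludes ulcers with signs of infection and active osteomyelitis at entry. A shift of about 3 points is small beside the plan's interval of 35.5% to 64.5% at n = 50. This limits the importance of the point, but the shift is systematic and a larger sample would not remove it.

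**Conclusion.** The point holds as a gap in the plan that has a predictable direction. Kaplan-Meier is named, exits that end any chance of observed closure are built into the protocol, and their handling is unstated. If they are censored, the week-12 closure estimate cannot fall below the on-study proportion and will usually exceed it.

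The size rests on assumed exit rates and timing. Under constant weekly rates and 4% to 10% exits, the excess is about 0.5 to 1.4 points at 25% closure, 1 to 3 points at 50% and 2 to 6 points at 75%. At 20% exits it is 3, 7 and 15 points. Early exits raise the largest value to about 18 points; exits that all follow the last closure bring it to zero.

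The curve is descriptive and secondary, and the primary proportion is not read from it. The change should be made, but the primary result does not depend on it.

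**What to change.** In the synopsis Statistical Analysis row, and in section 7 where the curve is now absent, replace the Kaplan-Meier sentence with wording such as: *Time to closure will be described by the Aalen-Johansen cumulative incidence of wound closure on study by 12 weeks after the index procedure. Exit for infection or osteomyelitis of the study ulcer, or death, is a competing event. Withdrawal of consent and loss to follow-up are censored at the last wound assessment. Median time to closure is reported only if the cumulative incidence reaches 50%.*

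The condition on the median is needed because the plan itself considers a closure rate of 25%, at which no median exists. Censoring withdrawal and loss to follow-up still assumes that those departures are unrelated to healing, and the text should say so.

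The cost is a few sentences and a slightly less favourable secondary curve. The Study Discontinuation CRF (section 6.10.6) already records when and under what conditions each subject exits, so no new data are needed. Standard software fits the estimator, and no clinical rule changes.

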
Study Design and Procedures
	
This is a multi-center post-market, single-arm, prospective follow-up study
 
Assessment and Roll-in Phase
 
Subjects will be recruited by the treating physicians, screened for eligibility, invited to participate in the study and provide informed consent. The subject's demographics, medical history, co-morbidities and wound characteristics will be documented and the subject will complete a SF-36 quality of life questionnaire. Subject will be instructed on proper nutrition.
 
Wound will undergo sharp debridement, be traced, photographed, and dressed per standard of care. Two tissue sections of at least 2mm will be retained for histological analysis. Subject will be fitted with and instructed on an offloading device. Subjects will return for MIRODERM treatment in two weeks.
 
Treatment Phase
 
On treatment day, wound will undergo sharp debridement, be traced, photographed and MIRODERM Biologic Wound Matrix will be applied. After treatment, subjects will be considered enrolled into the trial. Details of treatment will be documented.
 
Subject will present weekly for the next twelve weeks. The dressing will be changed and may undergo further MIRODERM treatment if indicated. The wound will be traced and photographed. Physician will document their assessment on whether the wound is 100% closed.
 
Subjects whose wound is completely closed at or prior to 12-weeks post-treatment, will be instructed to return 1-week following for a confirmation visit. Subjects whose wound is not assessed as closed by 12-weeks post-treatment, will have two tissue sections of at least 2mm collected, complete a quality of life assessment, and will then be discontinued per protocol.
 
Confirmation Phase
 
Subject will complete a quality of life assessment and have their wound area photographed. Physician will confirm the wound is still closed and the subject will be discontinued per protocol. If wound has reopened subject will return to the treatment phase.

Subject Participation
	
Subjects can be expected to reasonably participate in the study for a minimum of 9 weeks and a maximum of 15 weeks depending treatment course.

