If wound has not closed, the dressing will be changed (subsequent to any needed treatment as described in the above paragraph) and the subject will return the following week. If the wound is healed subject will return for a confirmation visit one week later. If, after 12 weeks, the wound is not healed, subject will complete a SF-36 quality of life survey, two tissue sections of at least 2mm from the wound area will be collected and the subject will be discontinued from the study per protocol.

Confirmation Phase

Subject will complete a quality of life assessment and have their wound area photographed. Physician will confirm the wound is still closed and the subject will be discontinued per protocol. If wound has reopened subject will return to the treatment phase.

Subjects whose wound has been assessed closed will return for a confirmation visit. The wound will be assessed for closure. If the wound is still closed, the wound area will be photographed, the subject will complete a SF-36 quality of life survey and be discontinued from the study per protocol. If wound has reopened, subject will return to the follow-up phase at the appropriate post-treatment week continuing there until wound closure or through 12 weeks of follow-up as described in “Treatment Phase” above.

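### Wound-area analysis loses subjects because they healed: confirmed closure ends follow-up, no later area is assigned, and missing data are ignored

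*Combined protocol and SAP*

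**What the plan says.** The Synopsis (Statistical Analysis) commits to a test on area: "A repeated measure ANOVA will be used to assess changes in, wound area and quality of life over time". Section 7 is looser on the method, "As appropriate a repeated measure ANOVA or Wilcoxon signed rank" test for each outcome measure, together with descriptive summaries. Its missing-data rule is unconditional: "Missing data will be ignored in statistical calculations while using the appropriate n (sample size) for any given statistic or test".

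On follow-up, section 6.9 ends participation when the "index wound has been determined to be fully closed and remains closed at their 1-week follow-up confirmation". Section 6.1 (Confirmation Phase) agrees: "the subject will complete a SF-36 quality of life survey and be discontinued from the study per protocol". Section 6.9 has a second exit related to outcome: "Subject presents with osteomyelitis of the study DFU or an infection of the study DFU".

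What is recorded when a wound closes is less clear.

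- **Tracing.** The Synopsis (Study Design and Procedures), section 6.7.2, Table 1 and section 6.10.17 ask for a tracing at follow-up visits and make no exception for closed wounds. Section 6.7.1, however, sends closed wounds to section 6.8.2, which asks only for a photograph. Section 6.10.18 treats photographs as qualitative.
- **Wound Assessment and Treatment CRF.** Table 1 schedules this form at follow-up, final and confirmation visits. Under section 6.10.4 it records closure status and gross dimensions. A zero is therefore available, or can be derived, at the closing and confirmation visits.

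No section says to derive that zero or to use it after exit.

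**The concern.** Follow-up stops because of the outcome being analysed. A subject whose ulcer closes at Week 7 has no area from Week 9 on, and the section 7 rule simply drops those weeks. The weekly means then come from changing sets of subjects, with the best responders removed first. A baseline to Week 12 signed-rank test loses the earlier healers. A classical repeated-measures ANOVA, which needs every visit, would lose them at baseline too. Section 7 does not say whether its appropriate n means complete cases or available cases.

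At stake is the reported change in wound area, which section 7 would test at 0.05, and with it part of the Synopsis objective on the course of healing. Section 4.3 words that objective as time to full closure and does not list area.

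**Working it through.** **Plan's own figures.** The documents give no sizing for wound area. The closure rates used here are those in section 7 ("The Confidence Intervals (CI) at selected success rates are as follows"). Clopper-Pearson limits at n = 50 with x = 12.5, 25 and 37.5 are 13.84–39.26%, 35.53–64.47% and 60.74–86.16%. These match the plan to rounding.

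**Closure timing.** The Synopsis gives participation of "a minimum of 9 weeks and a maximum of 15 weeks". Subtracting 2 weeks of roll-in and 1 week to confirmation gives 9 − 3 = 6 and 15 − 3 = 12, so closures fall at about Weeks 6 to 12. An even spread over these seven weeks is an assumption.

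**Formula.** Let c be the proportion closed by Week 12 and s the share of all subjects who have closed and have a recorded zero at Week 12. Let A be the mean area of open ulcers, with no other exits.

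- All subjects: mean = A(1 − c).
- Subjects with data: mean = A(1 − c)/(1 − c + s).
- Overstatement ratio = 1/(1 − c + s).

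If the closing and confirmation visits both carry a zero, Week 11 and Week 12 closers have a Week 12 value, so s = 2c/7. If only the closing visit does, s = c/7. If neither does, s = 0.

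| Zero recorded at | c = 25% | c = 50% | c = 75% |
|---|---|---|---|
| Closing and confirmation (s = 2c/7) | 1.22 | 1.56 | 2.15 |
| Closing only (s = c/7) | 1.27 | 1.75 | 2.80 |
| Neither (upper bound) | 1.33 | 2.00 | 4.00 |

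Example: c = 50%, s = 2 × 0.50/7 = 0.143, ratio = 1/(0.50 + 0.143) = 1.56. The number with a Week 12 area is 50 × 0.643 = 32.1 of 50 (28.6 if only the closing visit has a zero).

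**Effect on mean reduction.** Assume open ulcers end at a fraction r of baseline, with equal baselines. The reduction is 1 − r(1 − c) in all subjects and 1 − r(1 − c)/(1 − c + s) in those with data. At c = 50% and r = 0.50 this is 75.0% against 61.1% (s = 2c/7) or 56.2% (s = c/7), a shortfall of 13.9 or 18.8 points. At r = 0.25 the shortfall is 6.9 or 9.4 points.

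**Check under another healing model.** A simulation assumed baseline areas of 1–12 cm² (log-uniform), exponential area change with a subject-level rate (SD 0.15 per week), closure below 0.1 cm², and a zero at the closing visit only. At 50% closure the Week 12 mean was 1.04 cm² in available cases against 0.59 cm² with zeros carried forward, a ratio of about 1.8. At Week 4 the two means were equal, so the distortion grows with time.

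**Exits for infection or osteomyelitis.** Let a share e exit unhealed with area unchanged from baseline (assumption). As a fraction of baseline, the mean in all subjects is r(1 − c − e) + e. Ignoring missing data gives r(1 − c − e)/(1 − c − e + s). At c = 50%, r = 0.25 and e = 10%:

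- All subjects: 0.25 × 0.40 + 0.10 = 0.200.
- Plan as written: 0.10/(0.40 + 0.143) = 0.184 (−1.6 points), or 0.10/(0.40 + 0.071) = 0.212 (+1.2 points).
- Zeros carried forward for healers only, unhealed exits still ignored: 0.10/(0.40 + 0.50) = 0.111 (−8.9 points).

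At c = 50% the plan's bias changes sign at e of about 8–12% for r = 0.25 and 19–27% for r = 0.50.

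**The case against.** The strongest reply is that a closed wound obviously has area zero. Section 7's list of analyses is permissive, the CRF already records closure and gross dimensions at the closing and confirmation visits, and nothing forbids deriving the zero. Much of this stands. It makes the 1.33/2.0/4.0 figures an upper bound only. A reader might infer from the photograph-only wording of section 6.8.2 that healed subjects have no closing area at all, but Table 1 and section 6.10.4 do not support that. The zero still covers at most two visits, and nothing extends it past exit. The flexibility in section 7 concerns the choice of test, while the missing-data rule is not optional.

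A second reply is that losing healers can only work against the device. That holds if closure is the only reason for exit. Section 6.9 also removes infected ulcers, and with enough such exits the bias reverses.

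A third is that no changed test result has been shown. That is correct: the working shows shifted means and reductions, which depend on assumed timing, r and exit rates.

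A fourth is that carrying zeros forward alone could do more harm than the present rule. The −8.9 point result bears this out for that scenario, so the remedy must cover unhealed exits as well.

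**Conclusion.** The point holds for the secondary wound-area analysis. Followed as written, the plan removes subjects from later weeks because they healed. With zeros at the closing and confirmation visits, closures even over Weeks 6 to 12 and no other exits, the Week 12 mean area is overstated about 1.22, 1.56 or 2.15 times at 25%, 50% or 75% closure. The ratios are 1.27, 1.75 or 2.80 if only the closing visit carries a zero. The net direction cannot be stated in advance, because the documents give no rate for infection or osteomyelitis exits.

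Two stronger readings are not supported. One is that the main result is biased: a confirmed closure still counts in the primary proportion, and closure is the event in the Kaplan-Meier analysis. The other is that healers are certainly lost from every week: that follows only if the ANOVA is complete-case, which section 7 leaves open.

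**What to change.** In section 7, replace the missing-data rule for wound area with one that covers all enrolled subjects:

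1. Area is 0 cm² from confirmed closure through Week 12, derived from the recorded closure status. Observed areas are used if reopening is seen.
2. In the same main analysis, subjects who exit unhealed (infection, osteomyelitis, withdrawal, loss to follow-up) keep a stated value, for example the last observed area carried forward. A sensitivity analysis uses baseline area.
3. Because many Week 12 values will be exactly 0, the change test is based on ranks (signed-rank, baseline to Week 12), or that test is reported beside the ANOVA. Report n per week.

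Also reconcile sections 6.7.1 and 6.8.2 with the Synopsis, section 6.7.2, Table 1 and section 6.10.17 on whether a closed wound is traced.

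The cost is a few sentences and a corrected cross-reference, with no added visits, subjects or CRF fields. The downside is two untested assumptions: that closure lasts after exit, and that unhealed exits stay at their last area. The first could favour the device, and so could the second if those ulcers enlarge. Both should be stated with the result.
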